5.6 Device operation specifications

5.6.1 Study device management

- 1) The relevant training shall be received by the users before using the device. And the users shall be familiar with the use of the device with the ability to identify the abnormality of the device. The users shall avoid results errors caused by human factors.
- 2) Inspect visually whether the package of the device is complete or damaged before using.

5.6.2 Recycling of study devices

The sponsor is responsible for recycling the study devices after the termination or at the end of the trial. The "Device Recycling Form" shall be signed by both parties, and all related materials shall be counted at the end of the trial. For specific device recycling matters, please contact the project manager of this clinical trial.

Conduct device recycling as follows and count the quantities:

1. Used study products

Study products that are not invalid, damaged, defective or involved in adverse events, and those involved in adverse events but determined as definitely unrelated to adverse events according to the judgment of the investigator, can be destroyed according to the regulations of the study site after use, without any need for recycling. Destruction of study products shall be recorded.

2. Unused study products

After the termination of the trial, the sponsor will collect all unused investigational and control medical devices. At the end of the study, all related materials must be counted.

3. Defective devices and devices related to adverse events:

In the following cases, the device shall be recycled and the relevant form for recycling devices shall be filled in:

- Damaged or defective products;
- Products that fail or malfunction during the study;
- Products that cannot be used due to improper storage conditions;
- Products with incorrect information on the packaging, such as incorrect expiration date;
- Products related to adverse events, regardless of whether they are damaged, defective or faulty.

In addition, the paper outer packaging of the study device shall be not recycled.

5.7 Combined treatment (medication) specifications

Collect and record the combined medication before and after the use of the study device during the trial (the closest one to such use, twice in total), and the medication and the study device shall pass through the same vascular access (excluding oral medication); medication/treatment for adverse events.

5.8 Measures to control bias

1) The sponsor shall provide relevant training for the investigator prior to the initiation of the study, so as to ensure that the investigators fully understand the study process and

are proficient in using the study product.

- 2) The operation shall be performed in strict accordance with the operation methods and procedures stipulated in the study protocol during the study process. And the quality control and supervision shall be conducted properly by the clinical research associate (CRA) to ensure that the investigators operate and implement in strict accordance with the study protocol. The above measures shall be implemented throughout the implementation phase of the study to reduce mistakes or operational errors.
- 3) The subjects shall be screened in strict accordance with the inclusion and exclusion criteria of the trial protocol to reduce selectivity bias for subjects.
- 4) The clinical study shall be performed by selecting trials or controls in a random way to reduce trial bias caused by sampling error.
- 5) The data shall be recorded properly during the process of the study. When the study is completed, the data shall be retained and organized properly. When any data problem is found, the data manager shall confirm the data through the data challenge form to avoid the data error.

6. Statistical Considerations

6.1 Estimation of sample size

A total of 378 subjects are proposed to be enrolled in this clinical trial. This study is a non-inferiority design with parallel control. The equivalent products already available on the market (BD Pre-filled Flush Syringes) are selected as the control group device. The study intends to investigate that the overall performance of the investigational device group device for flushing and/or locking the catheter is non-inferior to that of the control group device. According to previous clinical experience, the overall performance success rate of equivalent devices for flushing and/or locking catheters is about 98%. Hence, it is assumed that the treatment completion rate of the investigational device group is consistent with that of the equivalent device. This study adopts a non-inferiority design, with α =0.025 (one-sided), β =0.1 (power of test of 90%), and the non-inferiority margin of 5%. The subjects in the investigational device group and the control group are allocated in an equal ratio of 1:1. The sample size shall be calculated to each enroll 165 subjects into the investigational device group and the control group by using the PASS software. However, 368 subjects shall be included to participate in this clinical study considering factors such as drop-out of subjects (drop-out rate of 10%) during the trial and other factors.

This study will be performed by 63 authorized nurses who participate in using the study device, each nurse will randomly use 3 investigational devices and 3 control devices, so a total of 378 subjects will be proposed to be enrolled in this clinical trial.

Minimum and maximum number of subjects and reasons for each clinical trial institution

This trial will be conducted simultaneously in multiple clinical trial institutions to enroll subjects. In principle, the subjects enrolled at each site will be distributed as evenly as possible to ensure adequate site representation. However, given the feasibility and enrollment progress, the number of subjects enrolled at each site will be properly adjusted according to the actual situation, so as to ensure the relative balance of the enrollment size of each site, and the final enrollment size of a particular site shall not exceed 50% of the total number of cases, and at least not less than half of the number of cases borne by the average distribution.

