18.1 Basic document management
18.2 Finance and insurance
Investigator's Statement

Abbreviations	Definition	
AE	Adverse Event	
CRC	Clinical Research Coordinator	
CRO	Contract Research Organization	
D	Day	
DMP	Data Management Plan	
eCRF	Electronic Case Report Form	
EDC	Electronic Data Collection	
FAS	Full Analysis Set	
GCP	Good Clinical Practice (Medical Device)	
ICF	Informed Consent Form	
MedDRA	Medical Dictionary for Regulatory Activities	
mL	Milliliter	
NMPA	National Medical Products Administration	
PASS	Power Analysis and Sample Size (Statistics Software)	
PPS	Per Protocol Set	
PT	Preferred term	
SAE	Serious Adverse Event	
SAS	Statistical Analysis System (Statistics Software)	
SOC	System Organ Class	
SS	Safety Set	
°C	Celsius	

List of Abbreviations

Synopsis

Study Title	A Prospective, Multi-center, Randomized, Open-label, Parallel-controlled Clinical Study of Pre-filled Flush Syringes
Protocol No.	MDS-21FLUSHCN01
Sponsor	BD Medical Technology (Jiangsu) Co., Ltd.
Study Sites	3 study sites
Planned Study Period	April 2022 to September 2023
Subject Population	Subjects requiring locking and flushing the end of catheter line at the intervals of different drug treatment.
Study Objective	To compare the BD PosiFlush [™] Pre-filled Flush Syringes (manufactured by BD, USA) with the pre-filled flush syringes (manufactured by BD Medical Technology (Jiangsu) Co., Ltd.) and evaluate the effectiveness and safety for locking and flushing the end of catheter line.
Study Design	This prospective, multi-center, randomized, open, and parallel- controlled clinical study is intended to evaluate the effectiveness and safety of pre-filled flush syringes. After signing of informed consent form, all subjects who meet the inclusion criteria and do not meet the exclusion criteria are randomized
	into the investigational group or control group in a 1:1 ratio. This study is performed by 63 trial nurses using the study device (investigational device and control device) to lock and flush the end of catheter line for all subjects, each nurse will randomly use 3 investigational devices and 3 control devices.
Number of subjects planned to be enrolled	 Sample size calculation assumptions: Overall performance success rate in the investigational device group is 98% Overall performance success rate in the control device group is 98% Non-inferiority margin is 5%
	 Allocation ratio of 1:1
	• Type I error rate is 0.025 one-side
	• Power is 90%
	• Attrition rate is 10%

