6.4 Statistical methods

This study will use SAS9.4 or above for statistical analysis. Statistical description shall be performed for all data, including baseline data, all effectiveness indicators, and all safety indicators, etc.

For quantitative variables, descriptive statistics will include number of subjects, mean, standard deviation, median, upper and lower quartiles, minimum, and maximum.

For qualitative variables, descriptive statistics will include the number of subjects and percentages.

Statistical test for the primary efficacy indicators is carried out with two-sided α =0.05. When P is less than 0.05, the inter-group difference is considered statistically significant.

Test hypotheses for the primary efficacy indicators:

Null hypothesis H₀: The overall performance success rate p_1 in the investigational device group is inferior to the p_2 of the control device group ($p_1 \le p_2$ - δ).

Alternative hypothesis H₁: The overall performance success rate p_1 in the investigational device group is non-inferior to the p_2 of the control device group $(p_1 > p_2-\delta)$.

Where $\delta = 5\%$ is the non-inferiority margin, which is the range of differences not considered clinically significant.

For the comparison of the main efficacy indicators between groups, the chi-square test or Fisher's exact test is adopted, and the confidence interval method is used for statistical inference to separately calculate the success rate of each group and the rate difference as well as two-sided 95% confidence interval between the two groups. If the lower limit of two-sided 95% CI > -5%, H₀ is rejected and the overall performance success rate of the investigational device group can be considered non-inferior to the control device group.

Descriptive analysis (quantitative or qualitative description) is performed for the secondary efficacy indicator, the safety evaluation indicators and other evaluation indicators. For categorical variables, summary statistics will include the number of subjects and percentage. For

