3.2 Study population and sample size

The study population includes subjects who require locking and flushing the end of catheter line at the intervals of different drug treatment. Specific inclusion and exclusion criteria are described in the 5.2 Selection of subjects of Protocol.

A total of 378 subjects are proposed to be enrolled in this clinical trial. The study is a parallel-controlled, noninferiority design in which the control device is the BD Pre-filled Flush Syringes, a kind of prevalent product already on the market. The study intends to investigate the overall performance of the test device for flushing and/or locking the catheter that shall be non-inferior to that of the control device. Based on previous clinical experience, the overall performance pass rate of control device for flushing and/or locking the catheter is about 98%, and the study assumes the same treatment completion rate for the test device and control device. This study adopts a non-inferiority design, with α =0.025 (one-sided), β =0.1 (power of 90%), and the non-inferiority margin is 5%. The test group and the control group are allocated 1:1 in equal proportions. The sample size shall be calculated by using the PASS software and 165 subjects shall be enrolled into each of the test group and the control group. However, 368 subjects shall be included in this clinical study considering factors such as dropouts (drop-out rate of 10%) during the trial and other factors.

This study will be performed by 63 authorized nurses who participate in using the investigational device, each nurse will randomly use 3 test devices and 3 control devices, so a total of 378 subjects are proposed to be enrolled in this clinical trial.

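### The plan states one-sided 2.5% error and 90% power together, but the Wald rule reaches 90% only by running at about 4%; rules that hold 2.5% have about 79–84% power

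*Protocol*

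**What the plan says.** Protocol 6.1 gives the design as one-sided alpha 0.025 and beta 0.1, with "power of test of 90%), and the non-inferiority margin of 5"%. It takes the control rate from experience: "the overall performance success rate of equivalent devices for flushing and/or locking catheters is about 98"%. The synopsis gives the same rate for the new syringe: "Overall performance success rate in the investigational device group is 98"%. Subjects are "allocated in an equal ratio of 1:1", and the result is 165 per arm: "The sample size shall be calculated to each enroll 165 subjects into the investigational device group and the control group by using the PASS software". This is raised to 368 for 10% drop-out and to 378 (189 per arm) so that each of 63 nurses uses three devices of each kind. SAP 3.2 repeats the pairing of one-sided 0.025 with "power of 90%), and the non-inferiority margin is 5"%. Neither document names the PASS procedure.

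Non-inferiority is declared when the lower limit of the two-sided 95% interval for the rate difference lies above -5% (protocol 6.4, SAP 6.3.1). Protocol 6.4 does not name the interval. SAP 6.3.1 specifies Wald, with Newcombe-Wilson only when both groups are at 100%. The per-protocol set is primary (protocol 6.2, SAP 5.2).

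**The concern.** A sample-size statement promises two things at once: a ceiling on the chance of passing an inferior device, and a floor on the chance of passing an equally good one. With success rates near 98% and a 5-point margin, the variance at the edge of inferiority is much larger than the variance where power is computed. A formula that uses only the smaller variance is then optimistic about one of the two promises. Which one breaks depends on the interval used in the analysis.

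Under the interval the SAP names, it is the error rate: a syringe with 93% success against 98% would be declared non-inferior in about 4% of trials, not 2.5%. If the interval is corrected so that 2.5% is honoured, it is the power, and the 90% printed in three places would then be wrong by about 11 points at the number expected after drop-out.

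**Working it through.** **Inputs.** From the documents: 98% in both arms, margin 0.05, one-sided alpha 0.025 (z = 1.960), power 90% (z = 1.2816), 1:1 allocation, 10% drop-out, 189 per arm enrolled. With 10% loss, 189 × 0.9 = 170 per arm are evaluable.

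**1. The plan's own figure.** The unpooled normal formula gives

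n = (1.960 + 1.2816)² × 2 × 0.98 × 0.02 / 0.05² = 164.8, so 165 per arm.

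For drop-out, 165 / 0.9 = 183.3, so 184 per arm and 368 in total. Both figures reproduce.

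**2. Where the approximation enters.** The formula uses one variance for both z terms.

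- At 98% v 98%: 2 × 0.98 × 0.02 = 0.0392.
- At the boundary, 93% v 98%: 0.93 × 0.07 + 0.98 × 0.02 = 0.0651 + 0.0196 = 0.0847.
- Ratio: 0.0847 / 0.0392 = 2.16.

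The score formula takes its alpha-term variance from rates restricted to the boundary (0.9383 and 0.9883): 0.9383 × 0.0617 + 0.9883 × 0.0117 = 0.0694. It then gives

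n = (1.960 × √0.0694 + 1.2816 × √0.0392)² / 0.05² ≈ 237.3, so 238 per arm.

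**3. Exact enumeration.** All pairs of binomial outcomes were enumerated. Power is at 98% v 98% and type I error at 93% v 98%.

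| Evaluable per arm | Wald (SAP 6.3.1): power / error | Newcombe-Wilson: power / error | Farrington-Manning: power / error |
|---|---|---|---|
| 165 | 89.8% / 4.1% | 78.7% / 2.0% | 75.0% / 1.9% |
| 170 | 89.1% / 3.8% | 78.8% / 2.2% | 78.8% / 2.2% |
| 189 | 91.9% / 3.9% | 83.6% / 2.1% | 83.6% / 2.1% |

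The Wald column includes the SAP's switch to Newcombe-Wilson when both arms are at 100%.

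**4. Along the boundary.** For control rates from 90% to 100%, with the new device 5 points lower, Newcombe-Wilson and Farrington-Manning stay at or below 2.5% at these three sizes. The Wald rule's error rises as the control rate nears 100%, to 8.1% at 165, 6.9% at 170 and 8.5% at 189.

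**5. Could another test recover 90%?** A linear programme bounded the power at 98% v 98% of any test whose error stays at or below 2.5% on the boundary (control rates 86% to 100%). The bounds are 81.0% at 165, 82.3% at 170 and 86.6% at 189. No choice of test delivers both stated figures, even with no loss.

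**6. Size for 90%.** Exact power is saw-toothed. It first passes 90% at 220 per arm with Newcombe-Wilson (90.9%; 88.8% at 219) and at 222 with Farrington-Manning (90.7%). About 220–230 evaluable per arm is a fair summary.

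**7. Sensitivity to the assumed rate.** With Newcombe-Wilson at 189 per arm and equal rates, power is 72% at 97%, 84% at 98%, 90% at 98.5% and 96% at 99%.

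**The case against.** The best defence is that the plan is coherent on its own terms. The formula behind 165 matches the Wald interval in the SAP, the arithmetic is right, and that rule does have about 90% power. All of this stands, and it limits the point in three ways.

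- A reader might infer that 165 or 368 is a calculation error. It is not: both follow from the stated inputs. What fails is a large-sample approximation near 98%.
- A reader might infer that, as planned, an equally good syringe would fail in about 21% of trials rather than 10%. The documents do not support this, because the SAP specifies Wald. Under that rule the chance of missing non-inferiority is 100 − 89.1 = 10.9% at 170 per arm and 100 − 91.9 = 8.1% at 189. The 21% (100 − 78.8) applies only once a rule that holds 2.5% is in use.
- A reader might conclude that the power figure alone should be rewritten. The documents would then report the power of a test that the SAP does not run.

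It can also be said that the shortfall hangs on a rate given only as about 98%. That is fair: at 98.5% and 189 per arm it almost vanishes, and at 97% it is larger. It remains true at the rate on which the plan bases its own claim.

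**Conclusion.** The point holds as a statement about the pair. At 98% v 98%, one-sided 2.5% and 90% power are not delivered together at 165, 170 or 189 per arm. Either the rule is Wald, with about 90% power and about 4% error at 93% v 98%, or it holds 2.5% and has about 79% power at 170 and 84% at 189. It does not show that the sponsor has understated the risk of a failed trial under the analysis as written; there the understated risk is a false claim of non-inferiority.

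The figures assume independent subjects, although each nurse contributes six uses, and they ignore the SAP's between-site test and site-weighted branch. The statement that Newcombe-Wilson and Farrington-Manning hold 2.5% is limited to control rates of 90–100% at the three sizes tabulated.

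**What to change.** Keep 378 subjects, and make the two changes below in one revision.

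- In SAP 6.3.1, use Newcombe-Wilson or a score interval for the primary comparison in all cases, not only when both arms are at 100%.
- In the synopsis, protocol 6.1 and SAP 3.2, replace 90% with the exact power of that rule: about 79% with 170 evaluable per arm after 10% loss, and about 84% with all 189. Add that 165 came from a normal formula using the same variance under both hypotheses.

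If the sponsor prefers to keep the Wald rule, leave power at about 90% and state in the same three places that the true one-sided type I error is about 4% at 93% v 98%, not 2.5%.

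The cost is wording in four places, or three if Wald is kept, and no extra subjects. Newcombe-Wilson is already in the SAP for the 100% case, so choosing it brings in no new method. The downside of the main option is a less favourable stated power; the downside of keeping Wald is an acknowledged error rate above the nominal one.

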6.2 Analysis data sets

Full analysis set (FAS): a data set consisting of all randomized subjects according to the basic principle of intention-to-treat analysis.

Per protocol set (PPS): refers to the subjects in the FAS who are of no serious violation against

the trial protocol, good compliance, and no missing primary efficacy indicators.

Safety set (SS): refers to the subjects who receive at least one study device treatment and at least one safety evaluation.

Efficacy analysis is to be performed based on the full analysis set and per protocol set. PPS will be used as the primary population for analyzing primary efficacy indicators in this study; FAS will be used as the population for analyzing the baseline data of this study, as well as for efficacy evaluation. SS will be used as the primary population for the safety analysis in this study.

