5.2 Per protocol set (PPS)

Dataset consisting of subjects in the FAS with no serious violations of the test protocol*, good compliance, and no missing primary effectiveness indicators.

PPS is used as the primary population for the analysis of the primary effectiveness indicators in this study.

Note: *"No serious violations of the trial protocol" refers to violations of the trial protocol that do not affect the primary effectiveness evaluation.

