6.3 Effectiveness evaluation

6.3.1 Primary effectiveness evaluation

(1) Evaluation Indicators

Overall performance of catheter locking and/or flushing is considered "**pass**" only if: Questions 1 to 4 are answered "Yes" and question 5 is answered "No".

Subjects who do not answer any of questions 1-5 or who answer "not applicable (NA)" will not be entered into the per protocol set; they will be treated in accordance with Table 6.1 when entering the full analysis set.

Table 6.1 Definition of "pass" for different scenarios of primary effectiveness indicators

Questions related to the primary effectiveness indicators	Scenario 1	Scenario 2	Scenario 3	Scenario 4
Whether the effectiveness evaluation is performed?	No	Yes	Yes	Yes
 Whether the air in the pre-filled flush syringe can be removed successfully? Whether the pre-filled flush syringe can be connected to the catheter smoothly? Whether the pre-filled flush syringe can flush and/or lock the catheter successfully? Whether the pre-filled flush syringe can be disconnected from the catheter smoothly? 	NA	Yes	At least one of the answers is "No" for questions 1-4, or "Yes" for question 5	At least one of the answers in Scenario 2 is "NA" or not selected
5. Whether any sites of the flush syringe leak at any time during use?		No		
Primary effectiveness determination (pass/fail)	Missing	Pass	Fail	Missing
Whether to be included in FAS	Yes	Yes	Yes	Yes
Whether to be included in PPS	No	Yes	Yes	No

(2) Evaluation method

The study hypotheses for the primary evaluation indicators are:

Null hypothesis H₀: The overall performance pass rate p_1 in the test device group is inferior to p_2 in the control device group ($p1 \le p2-\delta$);

Alternative hypothesis H₁: The overall performance pass rate p_1 of the test device group is not inferior to p_2 of the control device group $(p_1 > p_2 - \delta)$.

Where $\delta = 5\%$ is the non-inferiority margin, i.e., the range of differences considered not clinically significant.

FAS and PPS are used for evaluation.

Main analysis:

Describe the number and percentage of subjects for whom the two kind of pre-filled flush syringes are used to flush and/or lock the catheter successfully for groups in each study site and all study sites.

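### The PPS is the primary set and the FAS is analysed beside it, but the plan gives no consequence to a PPS pass with a FAS fail

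*Protocol*

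**What the plan says.** On the primary population the two documents agree. Protocol 6.2: "PPS will be used as the primary population for analyzing primary efficacy indicators in this study". SAP 5.2: "PPS is used as the primary population for the analysis of the primary effectiveness indicators in this study".

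The FAS is also used. Protocol 6.2: "Efficacy analysis is to be performed based on the full analysis set and per protocol set". SAP 6.3.1, for the primary endpoint: "FAS and PPS are used for evaluation".

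The success criterion is a single interval rule. In Protocol 6.4 it begins "If the lower limit of two-sided 95% CI > -5" (per cent), and H0 is then rejected. SAP 6.3.1 repeats it. Neither version names the set it applies to. Neither document makes the sets co-primary, requires them to agree, or says what happens if they disagree.

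PPS membership is governed by Protocol 6.3. It lists eligibility errors, a missing primary outcome, major violation with poor compliance, and a fourth, unspecified ground for other reasons. Individual exclusions are settled by discussion among the investigator, sponsor, data administrator and statistician. The trial is open-label (Protocol 5.1), and Protocol 8.8 marks blind review as not applicable. SAP Table 6.1 keeps a subject rated as failing in both the FAS and the PPS.

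**The concern.** In an open-label trial, those who settle the PPS can know both the arm and the nurse's rating. If the PPS and FAS disagree, the claim rests on post-randomisation exclusions, and the set that preserves randomisation has no stated role in the decision. The assumed success rate is high ("Overall performance success rate in the control device group is 98" per cent, with the same rate assumed for the test device), so few failures are expected and the interval moves noticeably with each one. A conflict would be visible, because both analyses are reported, but its meaning would have to be argued after the results are known.

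**Working it through.** **Inputs.** Synopsis: success 98% in both arms, margin 5%, one-sided type I error 0.025, power 90%, attrition 10%. Protocol 6.1: 165 per arm, 368 in total, 378 enrolled. SAP 3.3: 189 in the test group with 1:1 allocation. SAP 6.3.1: Wald interval for the pooled rate difference.

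**The plan's own figure.** n = 2 × 0.98 × 0.02 × (1.960 + 1.282)² / 0.05² = 164.76, so 165 per arm. 165 / 0.9 = 183.3, so 184 per arm and 368 in total. 63 nurses × 6 = 378, or 189 per arm. The sample size reproduces and is not in question. Expected failures are 0.02 × 189 = 3.8 per arm.

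**Can the two sets disagree?** Lower limit = (p1 − p2) − 1.96 × √[p1(1−p1)/n1 + p2(1−p2)/n2]. The failure counts below are assumed.

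| Set | Test failures | Control failures | Difference | Lower limit | Margin met? |
|---|---|---|---|---|---|
| FAS | 7/189 | 3/189 | -2.12% | -5.35% | no |
| PPS, one failed test subject excluded | 6/188 | 3/189 | -1.60% | -4.68% | yes |
| FAS | 8/189 | 4/189 | -2.12% | -5.64% | no |
| PPS, two failed test subjects excluded | 6/187 | 4/189 | -1.09% | -4.35% | yes |

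First row: p1 = 182/189 = 0.96296, p2 = 186/189 = 0.98413, SE = 0.01647, and -0.02116 − 1.96 × 0.01647 = -0.0535. Because Table 6.1 keeps failures in the PPS, each exclusion in the table needs a separate ground under Protocol 6.3.

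**How often would this arise?** With equal counts of 4 in 189 the lower limit is -2.90%. With 4 control failures, 7 test failures still pass (-4.97%). With true rates of 98% in both arms and 189 per arm, the chance that the full count fails and dropping one failed test subject turns it into a pass is about 4%.

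**Power of a both-sets rule.** By the normal approximation, power is 93.5% for the FAS (189 per arm, all evaluated) and 90.9% for the PPS (170 per arm, i.e. 10% excluded). The worst-case joint bound is 1 − 0.065 − 0.091 = 84.4% from these rounded figures (84.3% unrounded). The sets overlap heavily, so the true value is higher. Simulation with 98% true rates, 10% random PPS exclusion and all outcomes observed gives about 88% for both sets against 89% for the PPS alone.

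**Missing outcomes in the FAS.** SAP 6.1 bases percentages on non-missing data, Table 6.1 classes unanswered or not-applicable items as missing, and SAP 7.1 does not fill them. On that text, the FAS differs from the PPS only through excluded subjects who have an outcome. The SAS code in SAP 6.3.1, however, codes every value other than a pass as the second category, so any missing record in the input counts as a failure. With 4 observed failures per arm and 4 missing outcomes in the test arm only, the observed-data lower limit is -2.98% and the missing-as-failure limit is -5.64%. With 10% missing per arm counted as failures, the success rate falls to 0.98 × 0.9 = 88.2% and FAS power to about 33%.

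**The case against.** Naming one primary set in advance, consistently in both documents, is a legitimate choice, and the PPS is often defended as the cautious set for non-inferiority. There are safeguards. Failing is not itself a ground for exclusion. SAP 6.2.1 requires a listing of everyone left out of the PPS and of protocol deviations. The FAS result is reported for the same endpoint.

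The safeguards stand: they make a conflict visible and selective exclusion harder. They do not say what a conflict means. The argument for the PPS carries less weight here, because treatment is one syringe use followed for one hour, which leaves little non-compliance to dilute a true difference.

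A reader might infer two stronger things. The first is that the plan lets a claim stand despite a FAS failure. The documents do not say so: the rule names no set and SAP 6.3.1 evaluates both, so the outcome of a conflict is undefined. The second is that one or two subjects will normally decide the trial, for example because 6 against 3 failures already breach the margin. They do at 170 per arm (-5.17%), but at the planned 189 the limit is -4.66%, which passes. The smaller denominator applies to the FAS only if about 10% of its outcomes are missing and left out.

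**Conclusion.** The gap is real and limited. Both documents make the PPS primary, neither gives a FAS failure any consequence, and PPS membership is settled without blinding and with a catch-all ground. At the planned size, one exclusion can separate the two results (-5.35% against -4.68%), but only in an edge case of about 4% under 98% true rates. That figure and the tabulated counts are assumptions chosen to show sensitivity; they do not predict selective exclusion. The sample size is sound. The FAS test is not fully defined until the conflict between the SAP text and its code on missing outcomes is resolved.

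**What to change.** State in Protocol 6.2 and SAP 6.3.1 that non-inferiority is concluded only if the lower limit of the two-sided 95% interval exceeds -5% in both the FAS and the PPS. Exclusions could then no longer rescue a failed FAS result, even though the catch-all ground remains.

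In the same amendment, reconcile SAP 6.1, Table 6.1 and 7.1, which leave missing outcomes missing, with the SAS code, which would count them as failures. The both-sets rule should not be adopted without this step, because its cost depends on the answer.

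No new data, subjects or analyses are needed. The rule is slightly stricter: joint power is about 88% against 89% for the PPS alone, assuming 98% true rates, 10% random PPS exclusion and missing outcomes not counted as failures. If they are counted as failures, the loss could be large (FAS power of about 33% with 10% missing per arm).
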